We will power the study to detect a 250mL difference in calculated intra-operative blood loss between groups. This effect size has been used in the total hip literature, and it is considered to be a clinically significant difference in blood loss¹⁵. Our analysis shows that 12 patients are required in each arm of the study (24 patients total) to achieve 81% power with an independent-sample t-test and statistical significance set to alpha equal to 0.05. Expecting that 10-25% of patients will be excluded, we will aim to enroll a total of 30 patients in this study.

Patients aged 18 or younger will be screened for study eligibility

3. Interventions or Observations – what data are going to be collected and from what source?

Only anesthesiologists agreeing to participate in the study will be paired with the study surgeons. Anesthesia will be conducted in a standardized fashion. The anesthesiologist will perform a neuraxial block (epidural, spinal, combined-spinal epidural) as well as administer general anesthesia. A neuraxial block will be placed using bupivicaine. A balanced general anesthetic utilizing a combination of either isoflurane, sevoflurane with or without nitrous oxide, vecuronium, midazalam and either fentanyl, morphine or dilaudid as the narcotic will be used at the discretion of the anesthesiologist. If a combined-spinal epidural is unsuccessful and an epidural and/or spinal are successfully obtained, the patient will still be included in the study. Patients not receiving neuraxial anesthesia will be excluded from the study. Arterial and venous access will be obtained in the usual sterile manner for monitoring.

The blood pressure target will be 20-25% below baseline, which will be achieved primarily with the combination of the general anesthesia and the neuraxial anesthesia. For blood pressure above this range, the epidural will be dosed with a short-acting local anesthetic, and/or the depth of the general anesthetic and will be titrated as per the anesthesiologist's judgment. For hypotension below this range, intravenous pressors, crystalloid, colloid or blood will be given. The technique of induced hypotension will not be utilized during these cases. Additional maintenance IV fluids or colloid will be given to maintain urine output of at least 0.5-1ml/kg/hr. Toradol and IV acetaminophen may be given towards the end of the case per the anesthesiologist's discretion.

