Bilateral VRO will be performed as per the surgeon's routine practice. In general, the operative extremity will be prepped and draped in the usual sterile fashion. Prior to incision, the anesthesiologist will administer a loading dose of 100 mg/kg of EACA with a max of 4-5 grams up to 1 hour prior to incision. During the case, an infusion of 33 mg/kg/hr (max of 1 gram/hr) will be maintained. The use of EACA will be terminated at the end of the case. Patients randomized to the placebo arm will be

infused with a comparable volume of normal saline prepared by the pharmacy. All participating anesthesiologists will not be blinded in this study. A direct lateral approach to the femur will be used, and standard surgical techniques for intra-operative hemostasis will be utilized. The surgeon will perform bilateral femoral osteotomies and associated soft tissue surgery and pelvic osteotomy. After all hardware is placed, the wound will be thoroughly irrigated and suctioned. A deep drain will be placed on each operative side, and the wound will be closed in layers. Intra-operatively, a cell saver will be used, and the volume (mL) of auto-transfusion will be recorded.

Hematocrit levels will be monitored regularly in the post-operative period. As per protocol, a post-op hematocrit will be drawn in the PACU, and subsequently, daily labs will be obtained unless specified by the medicine or surgical attending. Routine, daily inpatient CBC data and drain output will be reviewed. Inpatient and office records will be accessed to help identify postoperative complications. The criteria for transfusion of blood products will be a hemoglobin level of < 7.0 g/dL or a hemoglobin level of < 10.0 g/dL with clinical signs of symptomatic anemia (e.g., unexplained tachycardia, hypotension unresponsive to fluids or vasopressors, change in mental status, low urine output, and shortness of breath). Blood will be administered 1 unit at a time, and the presence of symptoms or signs will be reassessed after each unit. This algorithm may be altered by the treating physician (e.g., PACU attending, surgeon, pediatrician, or the OR anesthesiologist), however all decisions will be supported by reasonable documentation. Drains will be removed on POD 2 unless specified by the attending surgeon, and the 24-hour clock will begin once the patient is in the PACU. All drains, patient charts, and patient rooms will be clearly labeled in order to identify study patients.

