All tests and imaging used in this study are considered standard of care.

Randomization Process:

The patients will be randomized into one of 2 groups: (1) Loading dose and infusion of EACA (2) Equivalent volume of normal saline prepared by the pharmacy. An EACA loading dose of 100 mg/kg with a max of 4-5 grams will be given up to 1 hour prior to incision. During the case, an EACA infusion of 33 mg/kg/hr (max of 1 gram/hr) will be maintained. The use of EACA will be terminated at the end of the case. Assignment of patients will be made based on a sequential treatment assignment or minimization strategy in order to ensure an even distribution of patients in each treatment arm. More specifically, each patient will be randomized to the treatment arm that would minimize differences between groups. Randomization will be stratified by sex and surgery type (bilateral VRO, bilateral VRO with associated soft tissue or osseous procedure) so that the number of male/female patients and VRO/associated procedure patients will be balanced in each study group between trial arms.

The Biostatistics Core of the HSS Healthcare Research Institute will randomize each patient based on the minimization strategy. It will be a double-blind experiment with all parties, except the pharmacy, anesthesiologist, and designated research assistant, being blinded to the randomization schedule (surgeon, medical staff, and patient). Patient recruitment will continue until a total of 30 patients are enrolled.

Treatment Groups:

Bilateral VROs will be performed as per the study surgeon's routine practice. In general, the operative extremity will be prepped and draped in the usual sterile fashion. Prior to incision, the anesthesiologist, will administer a loading dose of 100 mg/kg of EACA with (max of 4-5 grams) or an equivalent volume of normal saline prepared by the pharmacy. The loading dose may be give up to 1 hour prior to incision. During the case, an EACA infusion of 33 mg/kg/hr (max of 1 gram/hr) will be maintained. Only anesthesiologists agreeing to participate in the study will be paired with the study surgeons, and all anesthesiologists will be aware of a patient's randomization to the treatment or placebo group.

Outcome Measures

Primary outcome: Calculated total blood loss.

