The primary outcome of interest (calculated total blood loss) will be presented as a mean +/-standard deviation and compared between the EACA and placebo groups with a two-sample t-test. Multivariable linear regression models will also be used to adjust for any potential confounding due to total blood loss volume between arms after adjustment for age, sex, BMI, and anesthesia type. To adjust for any patients lost due to early withdrawal, we will increase our sample size by 3 patients in each group for a total sample size of 30 patients.

Calculated total blood loss will be determined from the difference between the preoperative hemoglobin and the postoperative hemoglobin (or the lowest postoperative hemoglobin during the hospital stay prior to transfusion). Based on hemoglobin balance, the estimated blood loss will be calculated according to the formula by Nadler et al.¹⁷:

```
Estimated Blood Volume (EBV) = (k_1 \text{ x Height}^3 \text{ (m)}) + (k_2 \text{ x Weight (kg)}) + k_3
For men, k_1 = 0.3669, k_2 = 0.03219, and k_3 = 0.6041
For women, k_1 = 0.3561, k_2 = 0.03308, and k_3 = 0.1833
```

Multiplying the EBV by the hematocrit (Hct) gives the red blood cell (RBC) volume. As such, a change in the RBC volume can be calculated from a change in the Hct level^{23,24}:

```
Total RBC volume loss = EBV \times (Hct Preop - Hct Postop)
```

Transfusions (mean volume per unit at HSS, 250 mL) can be taken into account by calculating the total blood loss¹⁶:

Total blood loss (L) = Total RBC volume loss + (No. of Units Transfused x 0.25) / (Hct Preop – Hct Postop) / 2)

All continuous secondary outcomes such as postoperative allogeneic blood transfusion requirement, intraoperative cell saver utilization, and length of hospital stay, will be analyzed in the same manner as the primary outcome.

Complications will be reported as incidence rates with 95% confidence intervals.

All hypotheses will be evaluated with two-sided tests with statistical significance set at $\alpha = 0.05$.

Bibliography

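### The additional regression adjusts for the anesthetic actually used, probably a post-allocation variable, so its EACA estimate could be biased in either direction; the unadjusted t-test is unaffected

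*Combined protocol and SAP*

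**What the plan says.** The primary endpoint is given under Outcome Measures in section 3: "Primary outcome: Calculated total blood loss". Section D, Data Analysis, has it "compared between the EACA and placebo groups with a two-sample t-test"; the sample-size list in the same section substitutes a Mann-Whitney test if normality fails. Regression is then added, to "adjust for any potential confounding due to total blood loss volume between arms after adjustment for age, sex, BMI, and anesthesia type". Nothing labels it supportive or says what happens if it disagrees with the t-test. Continuous secondary outcomes, including transfusion requirement, cell saver use and length of stay, "will be analyzed in the same manner as the primary outcome".

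Four statements in section 3 bear on the anesthesia covariate:

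- The block has three forms: "The anesthesiologist will perform a neuraxial block (epidural, spinal, combined-spinal epidural) as well as administer general anesthesia".
- It may change during the case: "If a combined-spinal epidural is unsuccessful and an epidural and/or spinal are successfully obtained, the patient will still be included in the study".
- The variable is listed among the operating room data as the anesthetic used, so it records what was delivered and not what was planned.
- The person delivering it knows the arm: "All participating anesthesiologists will not be blinded in this study", and under Treatment Groups "all anesthesiologists will be aware of a patient's randomization to the treatment or placebo group".

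Under Randomization Process, allocation is stratified by sex and surgery type. Surgery type is not among the regression covariates.

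**The concern.** A covariate in a randomized comparison should be fixed before allocation. Every included patient must have a neuraxial block, so what varies in anesthesia type is mainly epidural, spinal or combined. That is settled by someone who knows the assignment, and it depends partly on which block succeeds.

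If technique depends on arm, adjusting for it does one of two things. If technique itself affects loss, the model removes the part of the arm difference that passes through it. If technique is also chosen with the patient's expected bleeding in mind, the model makes the arms differ in bleeding risk within each technique group, even when technique has no effect on loss. A route from technique to loss is plausible on the protocol's own account, since section 3 relies mainly on the combined general and neuraxial anesthetic to reach the blood pressure target.

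The wording has a second fault: it names total blood loss, the outcome, as the source of confounding. In a transfusion or length-of-stay model blood loss would be a mediator, the route by which EACA is expected to act.

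At stake is the only adjusted estimate in the plan.

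**Working it through.** **Inputs from section D.** Difference 250 mL, SD 233.69 mL, 12 per arm, two-sided alpha 0.05. The documents give no technique frequencies and no technique effect on loss; both are assumed below.

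**The plan's own figure.** Standard error = 233.69 × √(2/12) = 95.4 mL; noncentrality = 250/95.4 = 2.62; df = 22. Noncentral-t power is 70.7% two-sided and 81.4% one-sided. The stated 81% is matched only by a one-sided test, whereas Data Analysis specifies two-sided tests. That is a separate matter and this point does not depend on it; two-sided tests are used throughout.

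**Shift from adjusting for technique.** Treat technique as one yes/no variable with effect g on loss and frequencies p1 (EACA) and p0 (placebo). Let the total EACA effect be −250 mL, including anything that passes through technique. If technique is otherwise unrelated to loss, the adjusted coefficient is

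−250 − g × (p1 − p0).

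- p1 = p0: −250, no bias.
- 20-point difference, g = −100: −250 + 20 = −230. The shift is 20/250 = 8%.
- 20-point difference, g = −200: −250 + 40 = −210. The shift is 40/250 = 16%.
- Difference in the other direction: −270 and −290.

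**Simulation with a larger, 40-point difference** (5,000 trials per row, 12 per arm, ordinary least squares). Unadjusted means in the same runs lay between −248 and −254 mL.

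| Technique, placebo/EACA | Technique effect (mL) | Formula | Simulated adjusted effect | Power, adjusted |
|---|---|---|---|---|
| 50%/50% | −100 | −250 | −251 | 68.9% |
| 30%/70% | −100 | −210 | −213 | 47.7% |
| 30%/70% | −200 | −170 | −172 | 32.7% |
| 70%/30% | −100 | −290 | −290 | 73.0% |
| 70%/30% | −200 | −330 | −331 | 83.2% |
| 30%/70% | 0, chosen partly on bleeding risk | n/a | −320 | 84.5% |
| 70%/30% | 0, chosen partly on bleeding risk | n/a | −180 | 40.1% |

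In the last two rows an unmeasured bleeding risk contributes 150 mL of the SD, and the propensity to receive the technique weights that risk and independent noise equally.

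**Power with pre-allocation covariates only.** Age, sex, BMI and surgery type are four covariates. If they explain nothing, df = 24 − 2 − 4 = 18 and power is 69.8%, against 70.7% with none. At 15 per arm the figures are 80.3% and 80.7%.

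**The blood-loss wording.** Outcome Measures makes calculated total blood loss the primary endpoint; the regression sentence calls it a source of confounding; the covariates that sentence lists are age, sex, BMI and anesthesia type. The first two conflict. The third shows that blood loss was not listed as a covariate, so the likely meaning is a comparison of blood loss between arms after adjustment for the four listed variables.

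**The case against.** The strongest reply is that the bias is hypothetical. No section says when the block is chosen relative to allocation. Section 3 describes anesthesia as standardized, and the discretion it grants refers to the general anesthetic agents, not the block. The fallback follows technical failure of a combined block, which nothing links to arm. All of this stands, and it is why the point is conditional.

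Nor does an imbalance alone show bias. At 12 per arm and 50% frequency, the standard error of a difference in proportions is √(2 × 0.25/12) = 0.20, and a gap of three or more patients arises by chance in about 31% of trials. Adjusting for a chance imbalance in a variable that affects loss improves the estimate. The difficulty is that the data from one trial of this size cannot separate chance from arm-aware choice. The 20 to 40 mL shift is also only 0.2 to 0.4 of the 95.4 mL standard error.

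It could be argued that adjustment is wanted, to remove the effect of unblinded behavior. The last two rows of the table show why it cannot be relied on to do so.

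Loss of degrees of freedom is not a reason to object: five covariates, counting two technique terms, still leave 69.5% power.

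A reader might infer that the plan adjusts blood loss for itself, or adjusts transfusion for blood loss, and so removes the EACA effect. The documents do not support that. Blood loss is not a listed covariate, regressing an outcome on itself is not a usable model, and "will be analyzed in the same manner as the primary outcome" most naturally means the same tests and the same four covariates. A simulation in which transfusion depends only on blood loss would return zero after adjustment by construction, so it would say nothing about this plan.

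**Conclusion.** The point holds in conditional form. A variable that allocation can influence sits in the only adjusted model. That its timing is post-allocation is a strong inference, not a stated fact. If technique comes to depend on arm, the adjusted estimate can move in either direction: by 20 to 40 mL (8% to 16% of 250 mL) with a 20-point difference and a 100 to 200 mL technique effect, and by about 40 to 80 mL with a 40-point difference. These inputs are assumptions. Without dependence on arm there is no bias. The unadjusted t-test, which carries the primary comparison, is untouched, and the regression is an additional analysis. The reference to confounding by total blood loss is a drafting error; it needs correcting chiefly so that nobody carries it into the secondary-outcome models.

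**What to change.** Replace the regression sentence in section D, Data Analysis, with:

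> As a supportive analysis, calculated total blood loss will be compared between arms by linear regression adjusted for age, sex, BMI and surgery type (the stratification factor); the same covariates, and not calculated blood loss, will be used for continuous secondary outcomes.

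This keeps the three prespecified baseline covariates, adds the stratification factor now missing from the list, and settles the regression's standing relative to the t-test. Remove anesthesia type from the model and tabulate the technique used by arm, so that any difference can be seen.

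The cost is one sentence and one table. Any precision that anesthesia type would have brought is given up, and the four covariates cost about one point of power at 12 per arm even if they explain nothing.

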Attending surgeons, orthopedic surgery residents, physician assistants and research assistants involved with this study will assist in data collection. For each patient, we will collect demographic data, pre-operative CBC data, intra-operative cell saver auto-transfusion volumes, post-operative number of packed red blood cell units transfused, post-operative CBC data, post-operative drain outputs, and post-operative complications. This information will be gathered from the peri-operative medical records and electronic medical records.

A sticker will be place on the front of each participating patient's chart identifying him or her as a study patient. Their enrollment will also be communicated in the clinician rounding notes for each patient. Drains will be labeled for each study participant as well, and nurses will record the drain outputs per their floor protocol.

Data recorded from the electronic medical record will include:

- Date of surgery
- Patient age at the time of surgery
- Patient sex
- Patient height (cm) and weight (kg) at time of admission
- Preoperative CBC data and coagulation study data

- Postoperative hemoglobin on all inpatient days postoperatively (g/dL)
- Transfusion requirement during inpatient stay (units required)
- Transfusion reaction
- Total 24-hour drain output
- Postoperative day and time of discharge
- Chart review of progress notes for evidence of clinically significant VTE
- Chart review of progress notes for evidence of reoperation, hematoma, seroma, or postoperative infection

Data recorded from the operating room record will include:

- Anesthetic used (e.g., spinal/epidural, general, etc.)
- Operative times (minutes)
- Intra-operative transfusion requirements (units of blood)
- Use of cell saver intraoperatively (auto-transfusion volume, mL)
- Intra-operative complications

Data recorded from outpatient postoperative office records will include:

- Chart review of progress notes for evidence of clinically significant VTE through six weeks post-operatively
- Chart review of progress notes for evidence of re-operation, hematoma, seroma, or postoperative infection through six weeks post-operatively

Patients will be randomized to either the intervention or control group, as per randomization protocol described elsewhere in the proposal. For patients who are randomized to the control group, study data will be collected in the same manner as for the intervention group.

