Secondary outcomes of interest: Postoperative transfusion requirements (allogeneic blood transfusion and intraoperative cell saver utilization), post-operative blood loss, length of stay, and post-operative complications.

Calculated total blood loss will be determined from the difference between the preoperative hemoglobin and the postoperative hemoglobin (or the lowest postoperative hemoglobin during the hospital stay prior to transfusion). Based on hemoglobin balance, the estimated blood loss will be calculated according to the formula by Nadler et al.¹⁷:

```
Estimated Blood Volume (EBV) = (k_1 \text{ x Height}^3 \text{ (m)}) + (k_2 \text{ x Weight (kg)}) + k_3
For men, k_1 = 0.3669, k_2 = 0.03219, and k_3 = 0.6041
For women, k_1 = 0.3561, k_2 = 0.03308, and k_3 = 0.1833
```

Multiplying the EBV by the hematocrit (Hct) gives the red blood cell (RBC) volume. As such, a change in the RBC volume can be calculated from a change in the Hct level^{23,24}:

```
Total RBC volume loss = EBV x (Hct Preop – Hct Postop)
```

Transfusions (mean volume per unit at HSS, 250 mL) can be taken into account by calculating the total blood loss¹⁶:

Total blood loss (L) = Total RBC volume loss + (No. of Units Transfused x 0.25) / (Hct Preop – Hct Postop) / 2)

The rate of perioperative blood transfusions, both intraoperative and postoperative, will be documented for analysis.

The criteria for transfusion of blood products will be a hemoglobin level of < 7.0 g/dL or a hemoglobin level of < 10.0 g/dL with clinical signs of symptomatic anemia (e.g., unexplained tachycardia, hypotension unresponsive to fluids or vasopressors, change in mental status, low

urine ouput, and shortness of breath). Blood will be administered 1 unit at a time, and the presence of symptoms or signs will be reassessed after each unit. This algorithm may be altered by the treating physician (e.g., PACU attending, surgeon, or the OR anesthesiologist), however all decisions will be supported by reasonable documentation. Drains will be removed on POD 2 unless specified by the attending surgeon. Of note, the chart of the patient will clearly indicate him/her as a study patient.

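### Even with its denominator read as a mean hematocrit, the primary-outcome formula is not a valid red-cell balance: no cell-saver term, units entered as pure red cells, no time limit on units

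*Combined protocol and SAP*

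**What the plan says.** Outcome Measures (in section 3) and Data Analysis (in section D) define the primary outcome, calculated total blood loss, identically. The postoperative value is the postoperative hemoglobin "or the lowest postoperative hemoglobin during the hospital stay prior to transfusion", with no rule for choosing between the two. Estimated blood volume (EBV) times the fall in Hct gives a red-cell volume. The next step is introduced by "Transfusions (mean volume per unit at HSS, 250 mL) can be taken into account by calculating the total blood loss", and its numerator is "Total RBC volume loss + (No. of Units Transfused x 0.25"). No unit Hct is applied, and no time limit is put on the units.

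The data list in section 3 has "Transfusion requirement during inpatient stay (units required"), "Intra-operative transfusion requirements (units of blood") and "Use of cell saver intraoperatively (auto-transfusion volume, mL"). The same section says that a cell saver will be used. Outcome Measures adds: "The rate of perioperative blood transfusions, both intraoperative and postoperative, will be documented for analysis". Cell-saver use enters the analysis only as a secondary outcome: "Postoperative transfusion requirements (allogeneic blood transfusion and intraoperative cell saver utilization").

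The denominator is printed as half the difference of the two Hcts, with unbalanced brackets. If the whole numerator is divided by it, every untransfused patient scores EBV × d ÷ (d/2) = 2 × EBV, however little they bled. That misprint is a separate matter. Here the denominator is read as the mean of the two Hcts.

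**The concern.** A red-cell balance needs three things: the red cells missing at a given sample, the red cells returned before that sample, and a common unit. The formula falls short on each.

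1. **Cell saver.** Salvaged cells were lost and then returned. With no term for them, the result is loss net of salvage, although the plan calls it total.
2. **Units as pure red cells.** The 250 mL is described as volume per unit, but it is added to a red-cell volume. Units given before the sample belong in the balance, only not at full volume.
3. **Timing.** A unit given after the chosen sample cannot have changed that sample's Hct. Such units may partly reflect later bleeding, since drains normally stay until postoperative day (POD) 2, but they do not measure it. The text permits the pre-transfusion low together with all units of the stay. Intraoperative units precede every postoperative sample and raise no timing problem.

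This is the only primary outcome in a trial of 30 patients, and two analysts could compute different values for the same transfused child. If EACA reduces bleeding, items 2 and 3 tend to enlarge the arm difference and item 1 to shrink it.

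**Working it through.** **Inputs from the documents:** 0.25 L per unit; EBV coefficients; target 250 mL; pilot SD 233.69 mL; 12 per arm required, 15 per arm enrolled; two-sided alpha 0.05.

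**Assumptions:** preoperative Hct 0.35 to 0.40; postoperative Hct 0.21 to 0.30 (the plan's transfusion criteria of 7 and 10 g/dL, at Hct = 3 × Hb); so mean Hct (0.35 + 0.21)/2 = 0.28 to (0.40 + 0.30)/2 = 0.35. Unit Hct 0.55 to 0.80. Cell-saver Hct 0.45 to 0.60.

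**The plan's own figure.** The stated 81% power at 12 per arm comes out at 70.7% with a two-sided t-test and 81.4% one-sided. That mismatch is separate and nothing here depends on it. At 15 per arm, two-sided t-test power is 80.7%, the baseline used below.

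**Cell saver.** An assumed 50 mL more return per patient in the placebo arm, at mean Hct 0.32, hides 50 × 0.45/0.32 = 70 mL to 50 × 0.60/0.32 = 94 mL of the arm difference.

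**Unit given before the sample.** Over-count = 250 × (1 − unit Hct)/mean Hct. At mean Hct 0.32: 250 × 0.20/0.32 = 156 mL (unit Hct 0.80) to 250 × 0.45/0.32 = 352 mL (unit Hct 0.55).

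**Unit given after the sample, if counted.**
- It adds 250/0.35 = 714 mL to 250/0.28 = 893 mL (781 mL at 0.32). One such patient moves an arm mean by 60 to 74 mL at 12 per arm, or 48 to 60 mL at 15.
- If bleeding had stopped, all of it is excess. If later bleeding removed exactly the unit's red cells, the excess at mean Hct 0.32 is still 156 to 352 mL.

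**Worked example.** Girl, 1.35 m, 30 kg, Hct 0.38 falling to 0.26.
- EBV = 0.3561 × 1.35³ + 0.03308 × 30 + 0.1833 = 2.052 L. Red-cell loss = 2.052 × 0.12 = 0.2462 L.
- No unit: 0.2462/0.32 = 769 mL.
- One unit after the nadir, counted: (0.2462 + 0.25)/0.32 = 1551 mL.
- Correctly paired later sample, no further bleeding, unit Hct 0.55 to 0.65: Hct rises to 0.327 to 0.339, the mean becomes 0.3535 to 0.3596, and 0.2462 divided by it gives 697 to 685 mL.
- Correctly paired later sample, all the unit's cells lost again (same unit Hcts): (0.2462 + 0.1375)/0.32 = 1199 mL to (0.2462 + 0.1625)/0.32 = 1277 mL.

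**Net direction.** Suppose 5 percentage points more placebo patients have one counted late unit: 0.05 × (156 to 781) = +8 to +39 mL of exaggeration. With the 50 mL cell-saver gap as well, the net is 8 − 94 = −86 to 39 − 70 = −31 mL. The sign depends on rates and volumes that the documents do not give.

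**Pilot check.** At mean Hct 0.32, late units at rate p, independent of other loss, add variance p(1 − p) × 781.25². At 5% this is 53% of 233.69²; at 10% it is 100.6%. If the pilot SD came from this formula, a 10% rate is ruled out at that Hct.

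**Power, if the pilot SD contains no late units.** A 5% rate in both arms gives SD = √(233.69² + 0.05 × 0.95 × 781.25²) = 289 mL. Simulation at 15 per arm (normal loss plus 781.25 mL at rate p, true difference 250 mL):

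| Late units | t-test | Mann-Whitney |
|---|---|---|
| none | 81% | 77% |
| 5% in both arms | 64% | 68% |
| 5% in placebo only | 85% | 81% |

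With 5% in both arms and no true difference, the t-test rejects 4.8% of the time.

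**The case against.** **The plan never says that later units are added.** This stands. The formula leaves the unit count undefined, and whole-stay units are also needed for the secondary outcome, so collecting them does not show that they enter the primary one. A reader might infer that the plan instructs the analyst to count them; it only permits it. Items 1 and 2 do not depend on this.

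**The 250 mL may have been meant as red-cell volume.** Then item 2 falls away. The text, however, says volume per unit, and the documents give no unit Hct. The range to 0.80 allows for dense units.

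**Cell-saver use is already analysed.** It is, as a secondary outcome. That does not turn the primary outcome into total loss.

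**The power loss is fragile.** This also stands. It needs a pilot SD free of late units and equal rates in the arms. With late units in placebo only, the effect is exaggerated and power rises. The two scenarios cannot both apply. Section D's Mann-Whitney fallback also softens the loss.

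**Randomization protects the comparison.** It protects the null as long as transfusion decisions do not differ by arm. Under Randomization Process the surgeon and medical staff are blinded. The anesthesiologist is not, and is among those who may alter the transfusion algorithm, so the condition is not guaranteed. This point does not rest on its failing.

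**Conclusion.** The point holds and should be fixed. As written, the formula omits recorded salvage and adds a product volume to a red-cell volume, and it leaves open whether units given after the sample count. Confidence is high for these defects of definition. The sizes rest on assumed Hcts: 156 to 352 mL over-counted per earlier unit, 714 to 893 mL added per later unit if counted, and 70 to 94 mL hidden by an assumed 50 mL cell-saver gap.

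Two stronger readings are not supported. One is that the formula favours EACA or raises the false-positive rate: the errors pull in opposite directions, the net sign is not determined, and simulated type I error stays near 5%. The other is that the trial is underpowered because of this: that follows only under the conditions above, and the documents do not say which formula produced the pilot SD, which they label intra-operative rather than total loss. What is at risk is the size of the estimated effect and its precision.

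**What to change.** In both Outcome Measures and Data Analysis, define:

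Total blood loss = [EBV × (Hct pre − Hct at sample) + allogeneic volume × a stated unit Hct + cell-saver volume × a stated Hct] ÷ mean of the two Hcts,

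counting only products given between the preoperative sample and the chosen postoperative sample.

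- Name one sample for all patients, transfused or not, from the CBCs already taken: for example the POD 2 CBC, or the last earlier one if it is absent. A fallback is needed because attendings may change the daily labs.
- Report the pre-transfusion-nadir version as a sensitivity analysis, counting only products given before it, and vary the product Hcts.
- Confirm whether the pilot SD of 233.69 mL came from the same formula.
- Settle this before unblinded data are seen.

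**Cost.** SAP wording plus chart look-up. Units, cell-saver volume, CBCs, height and weight are already collected, and no new test is needed.

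**Downsides to state in the SAP.** Transfusion times are not in the data list and must come from charts. Product Hcts are assumed. A sample taken after transfusion raises the mean-Hct denominator, so the same bleed reads about 72 to 84 mL lower in the worked example (769 against 697 to 685 mL). The nadir version avoids this but stops counting loss at the first transfusion.
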